**Table 2. Patient Demographic and Clinical Characteristic Variables at Index**

Variable	Operational definition
Age	Age will be defined as of the index date and will be used to assign patients to age groups: 18-29, 30-49, 50-64, 65-74, $\geq 75$ years and unknown/missing age.
Gender	Defined as of the index date as the distribution of female, male and unknown/missing sex patients.
Region	Kingdom of Bahrain
Nationality	Nationality of the patient will be mentioned
Enrollment Date Place of Service (POS)	Distribution of patients by the type of outpatient encounter during the enrollment date (eg, office visit, emergency room (ER), outpatient hospital, other, etc.).
Enrollment Date	Date (defined as MM/YYYY) of the enrollment date specified for each Cohort.

Variable	Operational definition
Specialty of Provider at enrollment Date	Distribution of the provider specialties present during the enrollment date. Patients with no provider specialty recorded will be included in an “Unknown/missing specialty” category.
Patient-reported COVID-19 symptoms	
List of COVID-19 symptoms to be added by study team (US, CDC definition).
 
1- Stuffy or runny nose 2- Sore throat 3- Shortness of breath 4- Cough 5- Low energy/tiredness/fatigue 6- Muscle ache/body aches 7- Headache 8- Chills or shivering 9- Feeling hot/feverish 10- Nausea or vomiting 11- Diarrhea 12- Loss of sense of smell 13- Loss of sense of taste

COVID-19 Symptom Onset Date	Date of symptom onset during the post-Paxlovid™ availability timeframe.
Time to COVID-19 Symptom Resolution	The number of continuous days with the same COVID-19 symptom. When available, the number of consecutive days will be reported as counts and percentages. The date of symptom resolution (last date recorded) will be reported when available.
Date of COVID-19 Vaccination	Date of each COVID-19 vaccination received. Note: patient-specific vaccination history may require more than 6-months pre-index time period.
Date of Paxlovid™ prescription written and/or fill history (eg, prescription claim)	Date of Paxlovid™ prescription written or fill history. Note: if both dates are available within the database, use the most recent date provided.

**Table 3. Clinical Characteristic Variables**

Variable	Operational definition
Comorbidities	A full list of comorbidities is detailed below and according to eCRF: Distribution of patients diagnosed with each comorbid condition during the baseline and follow-up periods. Comorbid conditions will include, but are not limited to, asthma, emphysema, chronic obstructive pulmonary disease (COPD), hypertension, diabetes, obesity, cerebrovascular disease, neurological disease, chronic kidney disease, chronic liver disease, malignancy, etc.
Risk Factors for Severe COVID-19	Distribution of patients with each of the following risk factors during the baseline and follow-up periods: 

• Age <math>\geq 50</math> years

• Obesity (BMI <math>\geq 30</math>)

• Chronic kidney disease (eGFR <math>\geq 30</math> ml/min)

• Diabetes Mellitus

• Primary and Secondary Immunosuppressive disease or immunosuppressive treatment

• Cardiovascular disease (including congenital heart disease) or hypertension

• Chronic lung diseases (for example, chronic obstructive pulmonary disease, asthma [moderate-to-severe], interstitial lung disease, cystic fibrosis, and pulmonary hypertension)

• Sickle cell disease

• Neurodevelopmental disorders (for example, cerebral palsy) or other conditions that confer medical complexity (for example, genetic or metabolic syndromes and severe congenital anomalies)

• Having a medical-related technological dependence (for example, tracheostomy, gastrostomy, or positive pressure ventilation [not related to COVID-19])

Death	Distribution of patients who died on or after the enrollment date in the follow up period.

PFIZER CONFIDENTIAL

CT24-WI-GL02-RF02 4.0 Non-Interventional Study Protocol Template For Secondary Data Collection Study

15-Jun-2022

Page 17 of 41

Variable	Operational definition
Inpatient Death	Distribution of patients who died during a hospitalization in the follow-up period.

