## **8. RESEARCH QUESTION AND OBJECTIVES**

The aim of this study is to describe the baseline demographic and clinical characteristics, and HRU of adult ( $\geq 18$  years) COVID-19 patients who have been prescribed nirmatrelvir, ritonavir treatment in the outpatient setting.

Primary objective:

1. To describe the baseline demographic and clinical characteristics, including pre-existing comorbidities, of adult COVID-19 patients treated with and those not treated with nirmatrelvir, ritonavir.

Secondary objectives:

1. To evaluate the number and proportion of COVID-19 patients who meet the most up-to-date WHO recommendations for the use of therapeutics in the treatment of COVID-19 (ie, version 14, published 10Nov2023) in comparison to Kingdom of Bahrain national recommendations.
2. To assess adult COVID-19 patients' HRU and outcomes within the 28-day period

Exploratory objective:

1. To assess HRU and outcomes at day 5, 7 and 21 as exploratory analyses

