### 9.2.2. Exclusion Criteria

**There are no exclusion criteria for this study.**

## 9.3 Variables

The following variables are used to obtain comprehensive descriptive results.

1. Demographics
2. Date of symptoms
3. Viral variant analysis where available (type of viral variant ie, omicron, delta etc.)
4. PCR date along with CT Value

5. Co-morbidities and
6. BMI if  $\geq 30$
7. Symptoms at presentation
8. COVID 19 vaccine status (NB 92% of population has been vaccinated -with at least one dose of COVID 19 vaccine- in Bahrain)
9. Hospital admission
10. Follow up looking at compliance and reason of non-compliance
11. Day 5,7, 21 and 28 symptoms for COVID-19 patients who receive and HRU limited to admission (ICU, ward, need for oxygen therapy) or death
12. Date of symptoms resolution if applicable

**Table 2** Table 2 below depicts the patient demographics that will be accessed during the baseline and follow-up periods. The baseline period is defined as one year before the index date. Comorbidities (full list in [Table 6](#)) and maintenance medication usage for chronic conditions (eg, statins, antihypertensives, etc.) will be described during the baseline period and follow-up periods and are listed in [Table 3](#).

Risk factors for severe COVID-19, intensive care unit (ICU) usage, invasive mechanical ventilation (IMV) usage, supplemental oxygen use, non-invasive ventilation, and high-flow nasal cannula usage are depicted in [Table 5](#) and will be extracted from the *I-Seha* national electronic health record database.

Where applicable, emerging treatment patterns may be assessed as the time from symptom onset to COVID-19 diagnosis, time from symptom onset to treatment initiation, and the time from COVID-19 diagnosis to treatment initiation as illustrated in [Table 5](#).

10Nov23 WHO recommendations for Paxlovid treatments to define: 1. COVID-19 patients who meet the WHO criteria for “strongly recommended” 2. COVID-19 patients who meet the WHO criteria for “conditionally recommended”, and 3. COVID patients who are not falling into categories 1 or 2 will be used.

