Antiviral Usage	Patients with antiviral therapy usage during the baseline and follow-up periods. Antiviral therapy usage will include remdesivir, nirmatrelvir/ritonavir (Paxlovid™) and molnupiravir.
Steroid therapy	Patients with steroid therapy during admission

PFIZER CONFIDENTIAL

CT24-WI-GL02-RF02 4.0 Non-Interventional Study Protocol Template For Secondary Data Collection Study

15-Jun-2022

Page 19 of 41

Variable	Operational definition
Treatment drugs being receiving at the Index date	Use Positive test as the INDEX Date and record use of any medicine listed in the potential DDI/Contraindications section of the EUA/Label

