### ANNEX 3. IMMUNOCOMPROMISED ICD-10 CODE LIST

Participants will be identified as immunocompromised (IC) if they had  $\geq 1$  hospitalization or  $\geq 2$  outpatient visits on separate dates with an ICD-10-CM code on a healthcare claim indicating an IC condition or if they had usage of specific immunosuppressive medications during the 12-month baseline period.

The list of ICD-10-CM codes used to identify IC cases by diagnosis and list of immunosuppressive medications are shown below in Table 9

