### Inferential statistics

Between-group differences in categorical variables will be examined using proportions tests, Chi-square tests of independence or Fisher exact tests as appropriate. Differences in continuous variables will be examined using independent t-tests.

Differences in proportions or means (as appropriate) and 95% confidence intervals between COVID-19 patients taking Paxlovid, and COVID-19 patients who were offered Paxlovid therapy but who refused treatment will be reported. Additionally, Cramer's V or Cohen's d will be reported.

Cramer's V is a measure of association that quantifies the strength and direction of the relationship between the two categorical variables being compared. Cramer's V ranges from 0 to 1, where 0 indicates no association between the variables, and 1 represents a perfect association. The magnitude of Cramer's V will be interpreted as follows:

Cramer's V	Effect Size
-------------------	--------------------

0.1	Weak
0.3	Medium
0.6	Large

Cohen's d quantifies the standardized difference between the means of the two groups, and is calculated by taking the difference between the means of the two groups and dividing it by the pooled standard deviation. The magnitude of Cohen's d will be interpreted as follows:

Cohen's d	Effect Size
------------------	--------------------

0.2	Small
0.5	Medium
0.8	Large

An a priori alpha level of 0.05 has been selected for all tests. As this work is exploratory no adjustment for multiple comparisons will be made.

PFIZER CONFIDENTIAL

CT24-WI-GL03-RF03 2.0 *Non-Interventional Statistical Analysis Plan For Secondary Data Collection*  
Study 01-Jun-2020  
Page 14 of 22

Selection of the control groups will consider the following characteristics based on the availability of data using propensity-score matched:

- age,
- sex,
- COVID vaccination status,
- high-risk status for severe COVID-19 outcomes (WHO definition),
- assessment of healthcare seeking behavior in 365 days prior to COVID infection (such as flu or streptococcus pneumoniae vaccine, has primary healthcare provider, number of primary care/hospital visits),
- socioeconomic factors (such as household income, employment status),
- geographic location of residence,
- comorbidities.

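### Comorbidities and risk factors are counted over baseline and follow-up, so conditions first coded after the index date can enter the patient description, the propensity match and the WHO tier

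*Protocol*

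**What the plan says.** - **Objective.** Protocol section 8 asks for baseline characteristics, "including pre-existing comorbidities, of adult COVID-19 patients".
- **Periods.** Protocol section 9.3 states: "The baseline period is defined as one year before the index date". Protocol Table 1 sets a 28-day follow-up from index.
- **Window for these variables.** Protocol Table 3 defines comorbidities as "Distribution of patients diagnosed with each comorbid condition during the baseline and follow-up periods" and risk factors as "Distribution of patients with each of the following risk factors during the baseline and follow-up periods". Section 9.3 says that comorbidities and maintenance medication "will be described during the baseline period and follow-up periods".
- **Immunosuppression.** Table 3 lists immunosuppressive treatment as a risk factor. Protocol section 9.7 gives chemotherapy and steroids as examples and refers to the immunocompromised code list. That list, in Annex 3, requires qualifying diagnosis codes or "usage of specific immunosuppressive medications during the 12-month baseline period". Protocol Table 5 separately collects "Patients with steroid therapy during admission".
- **SAP.** SAP Table 2 lists the same comorbidities and risk factors with no window. The shell for clinical characteristics (SAP Table 6) has one Paxlovid column, one control column, a p-value and an effect size. The propensity list in SAP section 1.13 includes comorbidities and WHO high-risk status, both undated, although it ties healthcare-seeking behaviour to the 365 days before infection.

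**The concern.** A condition first recorded after the index date is neither a baseline finding nor, on the record, a pre-existing one. Admitted patients are examined, coded and treated more than those who stay at home. A window that runs into follow-up therefore picks up more conditions in whichever group is admitted more often.

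Three uses are exposed:

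- **The primary, descriptive objective.** Prevalence is overstated, and a difference between groups can appear that did not exist at index.
- **The propensity match.** Matching on post-index codings conditions partly on the outcome being compared, because new codings follow admission.
- **The WHO tier.** The high and moderate tiers depend on immunosuppression and chronic conditions, so a post-index record can move a patient up a tier.

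**Working it through.** **1. Can the outputs keep the two periods apart?**

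- Protocol Table 8 has a single comorbidity row, under a heading for baseline variables.
- The SAP Table 6 shell has one column per group, no period split, and lists deaths in the same table as comorbidities.
- The SAP section on endpoints and covariates says it will use record variables that align with what the protocol requires. For these rows, the protocol's stated window is baseline plus follow-up.
- SAP section 1.2, objective (iii), names comorbidities among the characteristics compared over a five-day follow-up. That is also a post-index period.

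No sentence says that the periods are pooled, but no planned table would show them separately.

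**2. Immunosuppression: the passages side by side.**

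- Table 3: baseline and follow-up, with no exclusion of COVID-19 treatment. The technological-dependence item in the same list does carry such an exclusion.
- Section 9.7: steroids are an example of immunosuppressive treatment, with a pointer to the code list.
- Annex 3: the 12-month baseline only.
- Protocol Table 6: speaks of prolonged corticosteroid use.

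These cannot all be applied together. Annex 3 does not settle the window for diabetes, hypertension, obesity or chronic lung disease, for which Table 3 and section 9.3 are the written rule.

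**3. How large could the artefact be?** The plan gives no figure to reproduce, so this is an illustration.

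Inputs from the documents:
- about 3000 treated and 1000 control patients (protocol section 9.5);
- 3% admission for moderate risk, 6% for high risk and 0.5% for low risk (protocol section 9.7);
- an 88% relative reduction in hospitalization or death in the cited placebo-controlled trial (protocol section 7), borrowed here as an upper-end difference in admission;
- alpha 0.05 (SAP section 1.13).

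Assumptions:
- true prevalence b = 5% in both groups;
- a share s of admitted patients without the condition is newly flagged, s = 50% to 100%;
- nobody outside hospital is newly flagged;
- tests are two-sided, on the unmatched groups.

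Apparent prevalence = b + (1 − b) × h × s, where h is the 28-day admission rate.

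Control h = 3%; treated h = 3% × (1 − 0.88) = 0.36%.

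- s = 100%: control 0.05 + 0.95 × 0.03 = 7.85%; treated 0.05 + 0.95 × 0.0036 = 5.34%. Difference 2.51 points. Pooled proportion 5.97%, standard error 0.865 points, z = 2.90, p = 0.004. The chance of p < 0.05 is about 81%.
- s = 50%: control 6.42%; treated 5.17%. Difference 1.25 points, z = 1.51, p = 0.13.

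Sensitivity, for s from 50% to 100%:

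- b = 2%: 1.29 to 2.59 points. b = 10%: 1.19 to 2.38 points.
- Treated admission 50% lower instead of 88% (b = 5%): 0.71 to 1.42 points.
- Control admission 6% (b = 5%, 88% lower): 2.51 to 5.02 points.
- Control admission 0.5%: at most 0.43 points for any b from 2% to 10%.
- Equal admission of 3% in both groups: difference 0, but both groups read 6.4% to 7.9% instead of 5%.

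If only data on or before index are counted, the artefact is zero in every scenario, because b is the same in both groups. The effect on the matched comparison of outcomes was not calculated.

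**The case against.** The strongest reply is that the window wording describes two periods without merging them. Section 9.3 can be read as describing each period in turn. Protocol Table 8 places comorbidities under baseline variables. The SAP speaks of patients with pre-existing comorbidities (section 1.5) and of a medical history that led to the offer of treatment (study population). Protocol section 9.7 also lets the SAP modify the protocol, so Table 3 need not govern the match or the WHO tier. Finally, age, sickle cell disease or congenital disorders are not produced by a 28-day admission. A first coding of diabetes in that time would mostly be late recording of existing disease.

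Much of this stands. Pooling is an inference, and contamination of the match and tier is a possibility, not a stated rule. For most listed conditions the mechanism is unequal ascertainment, not disease caused by the admission. But the SAP does not use its freedom to set another window, and unequal ascertainment is enough to distort the comparison.

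A reader might go further and infer that steroids given in hospital are turned into baseline immunosuppression. The documents do not support that as a settled rule. Section 9.7 links immunocompromised status to the code list, the list is confined to the baseline year, Table 6 requires prolonged use, and in-hospital steroids have their own outcome row. What the documents show for this item is a conflict. A reader might also want to show inflated admission rates among flagged patients, but the SAP plans no analysis of outcome by risk factor. The between-group difference in prevalence is the relevant measure.

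**Conclusion.** The point holds as a defect in the variable window. The written rule for comorbidities and risk factors extends past index, against the primary objective, and nothing in the SAP tables, shells or propensity list restricts it. For immunosuppressive treatment, Table 3 and section 9.7 on one side and Annex 3 on the other must be reconciled.

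The size is uncertain. A false difference of roughly 0 to 2.5 points is plausible at 3% control admission. The upper end needs an 88% lower treated admission rate and every admitted patient newly flagged. The difference is negligible at 0.5% admission. The overstatement of prevalence does not depend on a difference in admission, only on some admitted patients being newly flagged and on the periods being pooled. True prevalence and the newly flagged share are assumptions, and the documents do not apply the admission rates or the 88% to this comparison.

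**What to change.** - In protocol section 9.3, protocol Table 3, SAP Table 2 and the propensity list in SAP section 1.13, state that baseline comorbidities, risk factors, the WHO and national classifications and all propensity covariates use only data recorded on or before the index date. Use the 12-month look-back of Annex 3, and any earlier record for items defined by history, such as cancer or smoking.
- Reconcile Table 3 and section 9.7 with Annex 3 for immunosuppressive treatment, so that one definition and one window apply.
- Align SAP objective (iii), so that comorbidities are not among the characteristics compared over follow-up.
- Report conditions and treatments first recorded in follow-up in a separate table, by group.

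The cost is a date filter in the derivation and short wording edits. Some existing disease that was first coded after index will be missed; the separate table shows how much. If the sponsor already intends to report the periods separately, the change only writes that down.

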**Table 4. HRU Data**

Variable	Operational definition
Hospital Length of Stay	The total length of stay (LOS) recorded for all hospitalizations during the baseline period and follow-up period in days (excluding within 24 hours of Paxlovid™ initiation).
ICU/Non-ICU LOS	The total number of days in the intensive care unit (ICU) and the number of days that were not spent in the ICU (non-ICU) recorded for all hospitalizations during the baseline period and follow-up period in days (excluding within 24 hours of Paxlovid™ initiation).
IMV/No IMV LOS	The total number of days with and without invasive mechanical ventilation (IMV) recorded for all hospitalizations during the baseline period and follow-up period in days (excluding within 24 hours of Paxlovid™ initiation).
Hospitalizations (Count and Percentage)	The count and percentage of patients with all-cause and COVID-related hospitalizations (excluding within 24 hours of Paxlovid™ initiation) during the baseline and follow-up period.
Number of Hospitalizations per Patient	The number of hospitalizations per patient in the baseline and follow-up periods for all-cause and COVID-related hospitalizations (excluding within 24 hours of Paxlovid™ initiation) will be described.
Number of Hospitalizations per Patient among Patients with Readmissions	The number of all-cause and COVID-related hospitalizations (excluding within 24 hours of Paxlovid™ initiation) per patient in the baseline and follow-up periods will be described among patients with readmissions during the same period. The cause for readmission will be reported when available.
Time to First Outpatient Encounter	Time from COVID-19 diagnosis to the earliest outpatient encounter to occur after diagnosis during the baseline period.

**Table 5. COVID-19 Disease Outcome Variables**

Variable	Operational definition
ICU Admission	Patients with ICU admission during COVID-related hospitalizations in the baseline and follow-up periods (excluding within 24 hours of Paxlovid™ initiation).
IMV Usage	Distribution of patients with IMV (ie, intubation and mechanical ventilation) usage, including extracorporeal membrane oxygenation (ECMO), during COVID-related hospitalizations in the baseline and follow-up periods (excluding within 24 hours of Paxlovid™ initiation).
Supplemental Oxygen Usage	Distribution of patients with supplemental oxygen usage during COVID-related hospitalizations in the baseline and follow-up periods (excluding within 24 hours of Paxlovid™ initiation).
Non-invasive Ventilation Usage	Distribution of patients with non-invasive ventilation usage during COVID-related hospitalizations in the baseline and follow-up periods (excluding within 24 hours of Paxlovid™ initiation).
High-flow Nasal Cannula Usage	Distribution of patients with high-flow nasal cannula usage during COVID-related hospitalizations in the baseline and follow-up periods (excluding within 24 hours of Paxlovid™ initiation).
Hospital Discharge Status	Distribution of patient discharge status for COVID-related hospitalizations during the baseline and follow-up periods (excluding within 24 hours of Paxlovid™ initiation). Discharge status should include transfer to skilled nursing facility, transfer to another healthcare facility, home, expired (dead), transfer to other long-term care facility, transfer to hospice based on the values recorded in the database.
Time from COVID-19 Test to Paxlovid™ Treatment	Time from the earliest COVID-19 test in the baseline period to the earliest date of Paxlovid™ prescription written date AND dispense date.
COVID-19 Lab Tests with Positive Result	The count and percentage of patients with a COVID-19 lab test with a positive result during the baseline and follow-up periods will be reported.
COVID-19 Lab Test with Variant Type	When available, the count and percentage of patients with each COVID-19 variant of concern (VOC) during the baseline period will be reported.
Monoclonal Antibody Usage	Patients with monoclonal antibody usage during the baseline and follow-up periods. Monoclonal antibody usage will include tocilizumab and bamlanivimab/etesevimab.
Antiviral Usage	Patients with antiviral therapy usage during the baseline and follow-up periods. Antiviral therapy usage will include remdesivir, nirmatrelvir/ritonavir (Paxlovid™) and molnupiravir.
Steroid therapy	Patients with steroid therapy during admission

PFIZER CONFIDENTIAL

CT24-WI-GL02-RF02 4.0 Non-Interventional Study Protocol Template For Secondary Data Collection Study

15-Jun-2022

Page 19 of 41

Variable	Operational definition
Treatment drugs being receiving at the Index date	Use Positive test as the INDEX Date and record use of any medicine listed in the potential DDI/Contraindications section of the EUA/Label

